## 6. Study population

### 6.1 Inclusion criteria - amended

1. Written informed consent signed before any study-specific procedure
2. Men or women aged 45 years and older
3. Established diagnosis of chronic heart failure NYHA class II-IV
4. Worsening heart failure requiring hospitalization for the initiation of intensification of heart failure therapy with **at least one** of the following
  - BNP  $\geq$  100 pg/mL or NT-proBNP  $\geq$  400 pg/mL (sinus rhythm) or BNP  $\geq$  300 pg/mL or NT-proBNP  $\geq$  1200 pg/mL (atrial fibrillation)
  - Radiographic evidence of pulmonary congestion (interstitial edema, pulmonary venous hypertension, vascular congestion, pleural effusion)
  - Catheterization documented elevated filling pressures at rest (left ventricular end-diastolic pressure  $\geq$ 15 mmHg or pulmonary capillary wedge pressure  $\geq$ 20 mmHg) or with exercise (pulmonary capillary wedge pressure  $\geq$ 25 mmHg)

OR

Ambulatory patients with a history of heart failure on individually optimized treatment with HF medications unless contraindicated or not tolerated, for at least 12 weeks and **at least one** of the following

- Hospitalization for heart failure within the past 12 months or
- BNP  $\geq$  100 pg/mL or NT-proBNP  $\geq$  400 pg/mL (sinus rhythm) or BNP  $\geq$  300 pg/mL or NT-proBNP  $\geq$  1200 pg/mL (atrial fibrillation)

---

 Inclusion criteria extended to ambulatory subjects with chronic heart failure as per Amendment 3 (Section 15.3)

5. For HFrEF only
  - EF  $\leq$  35% assessed by any imaging modality (e.g. echocardiography, cardiac magnetic resonance, cine levocardiography) within 12 months prior to study inclusion
6. For HFpEF only
  - EF  $\geq$  45% assessed by any imaging modality (e.g. echocardiography, cardiac magnetic resonance, cine levocardiography) within 12 months prior to study inclusion
7. Willingness to wear the DynaPort Move Monitor accelerometer belt and VitalPatch biosensor during the trial
8. Body size allows wearing of the accelerometer belt as confirmed by ability to comfortably fasten the test belt provided for the screening process

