## **10. Statistical methods and determination of sample size**

### **10.1 General considerations - amended**

All statistical details including calculated variables and proposed format and content of tables will be detailed in the Statistical Analysis Plan (SAP). The SAP will be finalized before study database lock. Statistical analysis will be performed using SAS or R; the versions used for both types of software will be specified in the SAP.

Statistical analyses will be of explorative and descriptive nature. The study is not aimed to confirm or reject pre-defined hypotheses; however, particular attention will be given to the ejection fraction (preserved versus reduced) as stratification factor.

All variables will be summarized with appropriate statistical methods: categorical variables by frequency tables (absolute and relative frequencies) and continuous variables by sample statistics (i.e. mean, standard deviation, minimum, median, quartiles and maximum).

Continuous variables will be described by absolute value and as change from baseline per analysis time point, as applicable.

Data from VitalPatch and DynaPort devices is expected to include missing values, as result of compliance in wearing the device. The amount of missing data within a day cannot be predicted and will be an outcome of the study. Missing data within day will be assessed by vendors according their validated algorithms of data pre-processing and quality check. No imputation will be performed in case day monitoring did not pass quality checks. The amount of missing monitoring will be assessed prior each statistical analysis and in presence of outliers the exclusion of subjects' data may occur.

All analyses will be performed for the FAS population (overall analysis) and separately for each participating country if subject numbers are sufficient and if required for local reasons.

Sample size and disposition information by analysis time point will be displayed in a frequency table.

All therapies documented will be coded using the World Health Organization – Drug Dictionary. Medical history, any diseases and AEs will be coded using the latest Medical Dictionary for Regulatory Activities (MedDRA) version.

No interim analyses are planned. The final analysis will be performed after end of the study which is the date the analytical dataset is completely available.

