- Explore the relationship between PA, 6-minute walking distance (6MWD), PRO, biomarkers, adverse events/clinical outcomes
- Investigate the accuracy of patients' self-reports (PRO, e.g. KCCQ) of time spent on PA in real life vs. objective assessment by the DynaPort Move Monitor and VitalPatch biosensor³

¹ Will not be addressed due to change from AVIVO to VitalPatch (ECG data only)

² Will not be addressed due to change in procedure schedule

³ Meaningful assessment not possible given the provided variables.

Given the data situation (not all parameters provided by the vendor) and the low number of subjects (recruiting stopped early due to recruiting issues), not all the original objectives mentioned above will be addressed.

3. Study Design

This is a non-randomized, multi-center, observatory prospective patient study. The study will be conducted in several centers in EU and non-EU.

[figure not shown]
Patients hospitalized due to heart failure as well as ambulatory patients with heart failure will be included in this study. Overall approx. 80 subjects have to complete at least all device monitoring periods:

- Approx. 60 subjects with established diagnosis of heart failure with preserved ejection fraction (HFpEF; EF ≥ 45%) (Cohort 1) and
- Approx. 20 subjects with established diagnosis of heart failure with reduced ejection fraction (HFrEF; EF ≤ 35%) (Cohort 2).

All patients will receive the AVIVO / VitalPatch biosensor at 5 monitoring periods (5 patches each subject in total, monitoring period 7 / 5 days each period) and the DynaPort Move Monitor (belt) at 2 monitoring periods (7 day monitoring each period). Results from both devices are not visible to investigator and subjects to avoid bias on treatment decisions.

Biomarkers will be investigated during the hospital stay (only in case patient is hospitalized), at visit 1, and at visit 4. A 6-minute walking test will be performed at visit 1 / discharge and after 11-12 weeks.

Design overview

Abbreviations: KCCQ = Kansas City Cardiomyopathy Questionnaire score; QS = Questionnaire for patient reported outcomes (daily and weekly); 6MWD = 6 minute walking distance; FUP = follow up visit

4. General Statistical Considerations

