4.1 General Principles

The statistical evaluation will be performed by using the software package SAS release 9.4 or higher (SAS Institute Inc., Cary, NC, USA).

All variables will be analyzed by descriptive statistical methods. The number of data available, mean, standard deviation, minimum, median, and maximum will be calculated for metric data. Frequency tables will be generated for categorical data.

The analysis will be based on the Clinical Pharmacology Standard (CLIPS), version 3.0 [2].

Tables and listings describing the impact of COVID-19 on the study will be created as appropriate. If needed, the onset of the COVID-19 pandemic will be considered as 11 MAR 2020 (date when the WHO declared the COVID-19 pandemic).

VitalPatch and AVIVO data will not be transferred to the clinical database and will be considered in the scope of the biomarker analyses.

All planned statistical analyses will be explorative. A confirmatory statistical analysis is not intended. Thus, no adjustment for the type I error level will be done.

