6.5.4 Wearable data

6.5.4.1 DynaPort

The analysis of the DynaPort data will be performed on on the DES population.

Summary statistics for the wearing time of DynaPort data will be presented by cohort and wearing period.

The following parameters (mean, minimum and maximum over wearing period) will be analyzed:

- Steps
- Physical Activity Level (PAL)
- Total Energy Expenditure (TEE)

- Active time (Sum of standing, shuffling, walking, stair walking and cycling time)
- Time spent in different activity states (sedentary / light / moderate / vigorous)

The DynaPort parameters mentioned above will be summarized by cohort/total and visit using descriptive statistics including arithmetic mean, SD, median, minimum and maximum.

Statistics will be presented for the original data and difference to baseline.

Graphical displays of individual data as well as mean values with standard deviations will be created for each parameter by cohort using planned sampling times.

The univariate LMM for the repeated values of the DynaPort parameters is

$$Y_{ij} = \mu + S_i + v_j + \beta base_i + E_{ij}$$

where μ is a constant common to all observations, S_i is the normally distributed random variable with mean zero and variance σ_d^2 corresponding to subject i , v_j is the fixed effect corresponding to visit j , and E_{ij} is a normally distributed random variable with mean zero and variance σ_e^2 , independent of S_i . The variable “base” is the baseline measurement included as covariate and β is the corresponding regression parameter.

Based on the described LMM, point estimates and 90% confidence intervals for the DynaPort parameters will be calculated.

Subgroup analyses will be performed for the defined categories (worsening / no worsening) of 6MWD, KCCQ and PRO.

7. Document history and changes in the planned statistical analysis

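### One untransformed normal mixed model gives 90% intervals for all DynaPort parameters; for zero-heavy ones such as vigorous time a visit-mean interval may under-cover, and, separately, the protocol's quartiles are dropped

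*SAP*

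**What the plan says.** SAP 6.5.4.1 lists steps, PAL, TEE, active time and "Time spent in different activity states (sedentary / light / moderate / vigorous", eight parameters when the four states are counted singly. Each is taken in three forms: "The following parameters (mean, minimum and maximum over wearing period) will be analyzed". One model is given for all of them, with a random subject term, a visit effect and a baseline covariate. The residual "is a normally distributed random variable with mean zero and variance" that is constant, and the subject term is normal too. Then: "Based on the described LMM, point estimates and 90% confidence intervals for the DynaPort parameters will be calculated". The SAP does not say whether the interval is for a visit mean or for a change.

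The section names no transformation, residual check or alternative analysis. The protocol had two safeguards: a log-scale analysis for biomarkers assumed log-normal (synopsis) and inspection of residuals (10.3.3.1, whose model covers device data). The SAP carries neither over.

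For descriptive statistics, protocol 10.1 promises "continuous variables by sample statistics (i.e. mean, standard deviation, minimum, median, quartiles and maximum". SAP 4.1 says: "The number of data available, mean, standard deviation, minimum, median, and maximum will be calculated for metric data". The DynaPort paragraph likewise has no quartiles, and SAP 7.2 does not mention the change.

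**The concern.** Eligibility requires "Established diagnosis of chronic heart failure NYHA class II-IV". In such patients vigorous activity may well be absent for most of a week. A variable that is zero in most patients, with a few skewed positive values, is far from the normal model. The interval for its mean then rests on one or two patients, can extend below zero minutes, and shrinks to 0-0 when nobody has any.

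Physical activity is the primary variable, and protocol section 5 intends the study to supply baseline values and standard deviations for planning later trials. Groups may be small: HFrEF was planned at 20, the SAP says recruitment stopped early, and SAP 6.5.4.1 also plans subgroups by worsening status. An interval labelled 90% that covers much less would mislead a reader who takes it at face value.

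Quartiles are a separate matter. For skewed data they are the usual robust measure of spread, and without them the tables leave only the SD and the range.

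**Working it through.** **Inputs.** From the documents: 90% level, normal terms, two wearing periods per patient ("the DynaPort Move Monitor (belt) at 2 monitoring periods (7 day monitoring each period"), and planned cohorts of 60 and 20. Assumed, because the documents are silent: 5-20% of patients have any vigorous time in a period; positive values are lognormal with log-SD 1 and mean 4 min/day (the mean only sets the scale and does not affect coverage); any/none status has latent correlation 0.6 across periods; n is 10 to 80. There were 20,000 simulated data sets per setting.

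**1. The plan's own figure.** With normal data the nominal 90% is reproduced: 89.6-90.1% for a single-visit mean, 90.0-91.1% with variance pooled over visits, and 89.7-90.4% for the visit difference.

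**2. One patient with any vigorous time.** If one of n patients has y minutes and the rest have none, the mean is y/n and the variance is (y² − y²/n)/(n − 1) = y²/n, so the standard error is also y/n. The t-interval is (y/n)(1 ± t). Since t exceeds 1, the lower limit is always negative. With n=10, y=4 and t=1.833, the interval is 0.4 × (1 ± 1.833) = −0.33 to 1.13 min/day.

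**3. Nobody with any.** The interval is 0-0 and misses a positive true mean. With a share p having any, the probability is (1 − p)^n. For p=10% this is 0.9^10 = 35% at n=10 and 0.9^20 = 12% at n=20. Coverage at n=10 therefore cannot exceed 65%.

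**4. Simulated coverage of the nominal 90% interval for a single-visit mean.**

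| n | 5-20% have any | 10% have any | Lower limit below 0 (10% have any) |
|---|---|---|---|
| 10 | 36-65% | 53% | 63% |
| 20 | 51-73% | 64% | 77% |
| 40 | 63-79% | 72% | 55% |
| 60 | 68-81% | 76% | 28% |

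Repeat runs differ by about 1-2 points. A random-intercept model pools variance over visits, which helps. The 5-20% range becomes about 49-74% at n=10 and 77-85% at n=60, and the 10% setting becomes about 65% and 81%. A second simulation with a different tail and pooled variance gave 71-85% with 80% zeros and 49-78% with 95% zeros, for n=10-80.

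**5. Where the shortfall does not appear.** With no true change, the interval for the visit difference covers 92-99% in the 10% setting and 90.2-99.8% over 50-95% zeros. A moderately skewed parameter (lognormal, log-SD 0.5) covers about 88-90% for a visit mean and 89.7-90.7% for the difference.

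**6. Period minimum.** The minimum over seven days is positive only if every day is. If a patient had vigorous time on half of days (assumed, days independent), the minimum would be zero with probability 1 − 0.5^7 = 99%; at 80% of days, 1 − 0.8^7 = 79%. So the minimum can be mostly zero even when the period mean is not.

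**7. Quartiles.** They do not enter the interval, so leaving them out changes coverage by 0 points.

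**Limits.** These are t-intervals without the SAP's baseline covariate. With that covariate, an adjusted visit mean covered the population mean only about 76-78% of the time even for normal data, because its standard error conditions on the observed baselines. That depends on the covariate and the target, not on skewness, and is not counted here.

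**The case against.** The decisive input is assumed: no section gives the share of zeros, the vigorous threshold or the achieved n. NYHA class II patients are eligible. Exclusion criteria 5 and 7 remove patients who depend on walking aids or are inactive for non-cardiac reasons, which could raise activity in those who remain. This stands, so the result is conditional. With half of patients having any vigorous time, single-period coverage is still only 77-85%.

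The study's question is three months against baseline, which points to the change, where coverage is at or above nominal. This also stands, but the SAP does not say that its intervals are for changes.

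The analyses are exploratory, SAP 4.6 allows documented changes after data review, and a negative or 0-0 interval is easy to spot. That lowers the stakes; it does not make the stated 90% correct. The protocol's examples for later sample-size work are movement intensity and daily steps, not vigorous time, and SDs come from the descriptive tables regardless of coverage.

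Protocol 10.3.1 and 10.3.4 themselves list summary statistics without quartiles, so the departure is from the general rule in 10.1 and the synopsis.

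A reader might infer that all DynaPort intervals cover far less than 90%, that dropping quartiles contributes to this, or that the spreads of HFpEF and HFrEF can no longer be compared. None of these is supported. The shortfall is confined to visit means of zero-heavy or very skewed parameters, quartiles play no part in coverage, and SDs and individual-data plots by cohort are planned.

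**Conclusion.** The point holds for zero-heavy parameters. SAP 6.5.4.1 applies one normal model with 90% intervals to all eight parameters, with no check or alternative. If 5-20% of patients have any vigorous time, a visit-mean interval covers about 36-65% at n=10 and 68-81% at n=60, or about 49-74% and 77-85% with pooled variance. This rests on the assumed zero share, tail and sample size, and on the interval being for a visit mean. No material shortfall was found for the visit difference or for a moderately skewed parameter, so there is no case here for abandoning the model for steps, PAL, TEE or active time.

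The missing quartiles are a separate and smaller departure from protocol 10.1 that affects description only.

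**What to change.** In SAP 6.5.4.1:

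- State whether each 90% interval is for a visit mean or for a change.
- Model moderate plus vigorous time as one parameter, and keep the mixed model for the other parameters.
- For vigorous time alone, and for any other parameter or period minimum that is zero in a large share of patients, report by cohort and period the number of patients with any (exact 90% interval), the paired change in having any, and the median and quartiles among those with any. Quartiles over all patients would not serve: with 5-20% having any, the expected result is 0 (0-0). The exact interval stays informative where the model gives 0-0: with 0 of 10 patients its upper limit is 1 − 0.05^(1/10) = 26%.

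Restore the first and third quartiles in SAP 4.1 and in the section 6 paragraphs that repeat its list.

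The cost is SAP wording and standard output options. The downside is that there would be no model-based mean for vigorous time alone.

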#### USE OF DIARY ITEMS TO VALIDATE ACTIVITY MONITOR

- Compare 1 week of activity monitor data with physical activity items from 1 week of diary monitoring
- Average diary data over 7 day period (must have  $\geq 4$  days to calculate a value)
- Physical Activity Diary Scores
  - Overall activity including carrying/lifting, walking outside, walking general, climbing stairs, housework, and exercise (average across items)
  - Individual item scores including general physical activity item
- Examine correlations between the activity monitor movement data and the physical activity diary scores

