This study aims to explore two devices providing a multi-marker biometrical monitoring including daily activity under real-life conditions in patients with HFpEF and HFrEF. It aims to identify potential new endpoints for future HFpEF trials by exploring clinically relevant changes over time and correlations/associations with conventional endpoints and biomarkers.

Furthermore, it aims to define the challenges and test the feasibility of this approach under real-life conditions.

This Statistical Analysis Plan (SAP) is based on the Clinical Study Protocol (CSP) No. BAY 1067197 / 19167, Version 4.0, dated 21 FEB 2020 [1].

2. Study Objectives

Primary objective:

- Measurement and quantification of daily physical activity (PA) in patients with HFpEF and HFrEF under real life conditions by activity tracker/belt and patch

Secondary objectives:

- Association between VitalPatch biosensor and DynaPort Move Monitor data (e.g. different levels of activity) to adverse events/clinical outcome data occurring during the study period
- Assess the baseline level and longitudinal changes over time of heart rate (HR), respiratory rate and ECG-derived parameters and the average of person-to-person physiological variability and the within-patient standard deviation between the baseline and 3-month measurements
- Assess the feasibility of activity tracking with two devices (VitalPatch biosensor and DynaPort Move Monitor) in patients with heart failure
- Correlation of activity data between VitalPatch biosensor data on activity and DynaPort Move Monitor¹
- Evaluate the relationship between physical activity levels, HR, respiratory rate and ECG-derived parameters and important measures in HFpEF; such as quality of life (QoL), patient reported outcome (PRO), biomarkers, outcomes (e.g. clinical endpoints such as hospitalization for heart failure, cardiovascular death, emergency visits)
- Support the development of HFpEF specific questions (PRO) for testing/validating cross-sectional and longitudinally
- Determine the variability of device derived biomarkers between subjects and within subjects over time in order to validate such biomarkers for clinical use in the context of heart failure
- Evaluate hs-copeptin as potential biomarker
- Correlation between patch monitor collected data and inpatient clinical data during hospital stay (e.g. echocardiography, weight gain/loss, NYHA, HR)²

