6.5 Other evaluations

If not stated otherwise, analyses will be performed on the FAS population.

For each parameter (6-minute walking distance, KCCQ, PRO), subjects will be split into classes representing clinically relevant worsening versus no relevant change or improvement. The exact definition will be given in the respective subsection.

6.5.1 6-minute walking distance

The 6MWD will be summarized by visit and cohort/total using descriptive statistics including arithmetic mean, SD, median, minimum, and maximum.

A frequency table will be created for the comparison of the subjects with and without observed worsening according to the following definitions:

- Worsening: decrease in 6MWD by at least 30 meters
- No worsening: decrease in 6MWD by up to 30 meters, no change or increased 6MWD

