6.5.2 Quality of life / PRO

6.5.2.1 KCCQ

The summary scores “Total Symptom Score”, “Clinical Summary Score”, and “Overall Summary Score” as well as the “Physical Limitation Scores” will be summarized using frequency counts by cohort and total.

A frequency table will be created for the comparison of the subjects with and without observed worsening according to the following definitions:

- Worsening: decrease in KCCQ score by at least 5 points
- No worsening: decrease in KCCQ score by up to 5 points, no change or increased KCCQ score

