6.5.2.2 PRO

The “Overall Activity Score” will be calculated as the sum of the following mean items: walking general, housework, and exercise.

The parameters

- Overall Activity Score
 - o General physical activity item (1 unit change on weekly average score)
 - o Physical activity impression of change item (2 unit change)
 - o Fatigue impression of change item (2 unit change)
 - o Shortness of breath impression of change item (2 unit change)
 - o Swelling impression of change item (2 unit change)

will be summarized using frequency count.

In addition, response with respect to the anchor measures derived from the following individual items

- General physical activity item (1 unit change)

- Physical activity impression of change item (2 unit change)
- Fatigue impression of change item (2 unit change)
- Shortness of breath impression of change item (2 unit change)
- Swelling impression of change item (2 unit change)

will be tabulated using frequency tables.

A frequency table will be created for the comparison of the subjects with and without observed worsening according to the following definitions:

- Worsening: decrease in “Overall Activity Score” by at least 2 units
- No worsening: decrease in “Overall Activity Score” by up to 2 points, no change or increased “Overall Activity Score”

The univariate linear mixed model (LMM) for the repeated values of the “Overall Activity Score” is

$$Y_{ij} = \mu + S_i + v_j + \beta base_i + E_{ij}$$

where μ is a constant common to all observations, S_i is the normally distributed random variable with mean zero and variance σ_d^2 corresponding to subject i , v_j is the fixed effect corresponding to visit j , and E_{ij} is a normally distributed random variable with mean zero and variance σ_e^2 , independent of S_i . The variable “base” is the baseline measurement included as covariate and β is the corresponding regression parameter.

Based on the described LMM, point estimates and 90% confidence intervals for the “Overall Activity Score” will be calculated.

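### DynaPort activity is related to 6MWD, KCCQ and PRO only through worsening / no-worsening subgroups; correlations with the continuous scores should be added

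*SAP*

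**What the plan says.** **Device analysis.** SAP 6.5.4.1 names eight DynaPort parameters: steps, PAL, TEE, active time, and time in each of four activity states. It summarises each descriptively by cohort and visit. It then fits a mixed model with subject, visit and the baseline value, and reports 90% confidence intervals. The section closes with: "Subgroup analyses will be performed for the defined categories (worsening / no worsening) of 6MWD, KCCQ and PRO". The model has no term for the class, and no between-class contrast is specified.

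**Classes.** Under SAP 6.5, "subjects will be split into classes representing clinically relevant worsening versus no relevant change or improvement". The three cut-points are:
- 6MWD: "Worsening: decrease in 6MWD by at least 30 meters"
- KCCQ: "Worsening: decrease in KCCQ score by at least 5 points"
- Diary: "Worsening: decrease in “Overall Activity Score” by at least 2 units"

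Everyone else (smaller decrease, no change, any increase) forms the other class.

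**Objectives.** SAP section 2 lists "Explore the relationship between PA, 6-minute walking distance (6MWD), PRO, biomarkers, adverse events/clinical outcomes". A second objective there relates physical activity levels to quality of life and PRO. Neither carries a footnote. Three other objectives are individually footnoted as not addressed or not meaningfully assessable. A general sentence adds that, given the available parameters and low recruitment, not every objective will be addressed.

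**Protocol.** Section 10.3.3.2 planned canonical correlation of device data with a set that includes 6MWD and KCCQ. Appendix 16.1 planned: "Examine correlations between the activity monitor movement data and the physical activity diary scores". SAP 7.2 gives reasons for a broad revision of the planned analyses but does not say which were removed. SAP 4.1 refers VitalPatch and AVIVO data to separate biomarker analyses; it does not do so for DynaPort.

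**The concern.** The study is meant to find out whether device-measured activity moves with conventional endpoints. Cutting a continuous change score in two weakens the view of that association in two ways. Subjects far beyond the cut-point count the same as those just past it. And because stable and improved subjects share one class, a rise in activity that accompanies improvement cannot be seen. A level-to-level question, such as whether subjects who walk further in six minutes also take more daily steps, has no planned analysis at all. With recruitment stopped early, the worsening class may also be small. What is at stake is how precisely and how fully the study can answer one of its listed questions. Type I error is not at issue, since SAP 4.1 declares all analyses exploratory and unadjusted.

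**Working it through.** The documents give no effect size, SD, worsening share or information figure, so there is no stated number to reproduce.

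**Inputs.** The cut-points are those of SAP 6.5.1 to 6.5.2.2. The target of 80 subjects is from Protocol 10.4. The SAP says the number is lower but does not give it, so N = 40 is assumed as an illustration. The worsening share p is assumed: 10% to 50%, with 5% as a sensitivity value.

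**Formula.** For a linear association and a normal change score X, the split retains the squared correlation between X and its class indicator:

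E(p) = φ(z_p)² / [p(1 − p)], loss = 1 − E(p).

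- p = 50%: 0.3989² / 0.25 = 0.637, loss 36.3%
- p = 20%: 0.2800² / 0.16 = 0.490, loss 51.0%
- p = 10%: 0.1755² / 0.09 = 0.342, loss 65.8%
- p = 5%: 0.1031² / 0.0475 = 0.224, loss 77.6%

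The loss reaches two thirds at p = 9.6% and is never below 36.3% under normality.

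**Effective sample size, N × E(p), and illustrative power** (assumed r = 0.3, two-sided 0.10 to match the 90% intervals). The continuous analysis uses Fisher's z. The split uses a two-class mean difference of r·φ(z_p)/[p(1 − p)].

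| N | Analysis | Effective N | Power |
|---|---|---|---|
| 80 | continuous | 80 | 86% |
| 80 | split, p = 50% | 50.9 | 71% |
| 80 | split, p = 20% | 39.2 | 61% |
| 80 | split, p = 10% | 27.4 | 48% |
| 40 | continuous | 40 | 59% |
| 40 | split, p = 50% | 25.5 | 47% |
| 40 | split, p = 20% | 19.6 | 39% |
| 40 | split, p = 10% | 13.7 | 30% |

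**Sensitivity to the share.** For the 30 m cut-point, assumed mean 6MWD changes of 0 to 40 m with SDs of 40 to 100 m give p from 4% to 38% and losses from 38% to 81%. Eleven of the 12 combinations lie between 38% and 65%.

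**Sensitivity to shape** (p from 50% to 10%, simulated). Losses are 46–65% for t with 5 df, 61–70% for t with 3 df, 50–62% for Laplace and 25–73% for uniform.

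**Timing.** In Protocol Table 9–1 the DynaPort periods are Days 9–16 and 77–84, while 6MWD is measured on Days 0 and 84. KCCQ is collected on Days 0, 16 and 84, so its Day 16 value is closer to the first DynaPort period. The diary runs alongside the DynaPort periods.

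**The case against.** Several points on the other side stand.

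- **The classes have a basis in the protocol.** Appendix 16.1 plans responder definitions from anchor measures with unit thresholds, and the protocol stresses clinically relevant change. Comparing activity across classes of relevant worsening resembles that aim, and the efficiency of a linear correlation is not the yardstick for it. This supports keeping the classes. It does not supply the missing continuous analysis.
- **The objectives may not be fully live.** The general caveat in SAP section 2 and the revision noted in SAP 7.2 leave room for the sponsor to have dropped the correlations. A reader might infer that the SAP firmly retains these objectives. The documents support only that it lists them without an individual footnote.
- **The diary limb is weaker.** A reader might take the missing monitor–diary correlation as unexplained. However, footnote 3 in SAP section 2 says that comparing self-reported activity time with the devices cannot be done meaningfully with the variables provided. The 6MWD limb is not touched by that footnote. For KCCQ, which the footnoted objective names as an example, what it rules out is the accuracy of self-reported time, not an association between scores.
- **Very small cells are not established.** A reader might compute 4 worsening subjects from 20 HFrEF subjects at 20%. The subgroup sentence does not say that classes are further split by cohort, 20 is a target, and 20% is assumed.
- **Correlations do not cure small numbers.** At n = 20 and r = 0.3, the 90% interval is tanh(0.310 ± 1.645/√17), about −0.09 to 0.61. By-cohort coefficients would say little.

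**Conclusion.** The point holds as a gap that is cheap to close. The only analysis tying DynaPort to 6MWD, KCCQ and PRO is a two-class display that hides improvement, and level-to-level association is not analysed. If 10% to 50% of subjects worsen, changes are near normal and the association is linear, the split loses about 36% to 66% of the information on the change-to-change association, and more below about 10% worsening. All three conditions are assumptions.

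A reader might infer that the plan discards a third to two thirds of the information on the whole objective. The documents do not support that. The figure concerns only the association between changes, the objective also spans biomarkers and clinical events, and no worsening share is stated. The scores themselves remain in the database. The effect is on precision and completeness in an exploratory study, not on validity.

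**What to change.** Keep the worsening classes in SAP 6.5.4.1 as a clinically anchored descriptive display. For each DynaPort parameter, using the mean over the wearing period as the SAP defines it, add a Spearman correlation with a 90% confidence interval, pooled over cohorts with adjustment for cohort:

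1. cross-sectionally with continuous 6MWD and KCCQ, and with the Overall Activity Score where the provided variables allow;
2. between the change from the first to the second DynaPort period and the continuous change in the same scores.

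Name the KCCQ score used, since SAP 6.5.2.1 summarises four. State which visits are paired. Note that DynaPort change runs from Days 9–16 to Days 77–84 while 6MWD change runs from Day 0 to Day 84, and that the Day 16 KCCQ lies closer to the first DynaPort period. Show by-cohort results only as scatter plots or descriptively. If the sponsor prefers not to add these analyses, SAP 7.2 should say that they were dropped.

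In the same edit, reconcile the class boundaries: a decrease of exactly 30 m, 5 points or 2 units currently fits both definitions.

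The cost is one paragraph and one exploratory table on data already collected. With one KCCQ score and one cross-sectional time point it holds 8 parameters × 3 scores × 2 analyses = 48 estimates, none adjusted for multiplicity, and should be labelled so.
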